7.22.5.2 Eliciting Adverse Events

Patients should be asked non-leading questions (eg, “How do you feel?”) and further questions should be posed if there is indication of an AE. The questioning should be conducted with due regard for objectivity and, in particular, the questioner should gather information regarding AEs from questioning the patient, the patient’s parent/guardian, spontaneous report by the patient or parent/guardian, laboratory reports, and any health care provider’s observations.

The onset date, resolution date, treatment administered, and outcome of each AE must be recorded on the appropriate eCRF. The relationship of each AE to study medication must be recorded. In addition AEs may be considered to be related to the IDDD, the IDDD surgical procedure, or the IT administration process. Since the AE may be deemed to be related to more than one of these factors, as many of these IDDD-related options as apply should be indicated on the eCRF.

7.22.5.3 Protocol Deviations for Medical Emergency or Adverse Event

During and following a patient’s participation in the study, the investigator should ensure that adequate medical care is provided to a patient for any AEs, including clinically significant laboratory test results.

The investigator should inform the patient, the patient’s parent(s), or the patient’s legally authorized representative when medical care is needed for intercurrent illness(es) of which the

investigator becomes aware. In an emergency situation, the investigator should contact the Shire Medical Monitor (see Section 7.22.5.1).

Only when an emergency occurs that requires an immediate deviation from the protocol for the safety of a patient, will there be such a deviation and this will be only for that patient.

The investigator or other physician in attendance in such an emergency must contact the Shire Medical Monitor as soon as possible.

The investigator, along with the Shire Medical Monitor, will make a decision as to whether or not the patient should continue in the study prior to the next scheduled dose. The departure from the protocol and the grounds for it should be stated in the eCRF.

7.23 Abuse, Overdose and Medication Errors

Abuse, misuse, overdose or medication error must be reported to the sponsor according to the SAE reporting procedure whether or not they result in an AE/SAE as described in Section 7.22.

- **Abuse** – Persistent or sporadic intentional intake of investigational medicinal product at a dose higher than prescribed per protocol (but below the dose defined for overdose) or when used for non-medical purpose (eg, altering one's state of consciousness)
- **Misuse** – Intentional or unintentional use of investigational medicinal product other than as directed or indicated at any dose, which is at or below the dose defined for overdose (Note: This includes a situation where the test article is not used as directed at the dose prescribed by the protocol.)
- **Overdose** – Overdosage with adverse clinical consequences is not anticipated with the use of HGT-1410. Additionally, HGT-1410 will be given in a clinical setting by a health care provider.
- **Medication Error** – A mistake made in prescribing, dispensing, administration and/or use of the investigational medicinal product.

7.24 Safety-related Study Stopping Rules

If any patient experiences a life-threatening (Grade 4) adverse event or death which is considered by the sponsor to be possibly, probably, or definitely related to study drug **or the IDDD**, or if 2 or more patients experience a Grade 3 adverse event during the trial that is considered by the sponsor to be possibly, probably, or definitely related to the study drug **or the IDDD**, then the site will be instructed to halt further HGT-1410 administration to all patients and the safety data reviewed. Following a review of safety data, the study will be either:

- Resumed unchanged
- Resumed with modifications to the protocol or
- Terminated

Patient safety will be monitored on a continuous basis during this study until the last patient completes his or her last scheduled study visit/assessment.

7.25 Pregnancy

Pregnancy and breast feeding are exclusion criteria. Only female patients who have reached menarche will be tested for pregnancy in HGT-SAN-067. If applicable, this will occur at study start and before each dose of HGT-1410 throughout the study. Pregnancy testing will be performed on a blood or urine sample. Patients with a positive or inconclusive result will not be eligible for this study.

At study start, a pregnancy test will be performed if more than 30 days have passed since the initial screening sample. Throughout the study pregnancy testing will occur prior to each dose of HGT-1410. The clinical site's local laboratory will analyze and report all pregnancy testing results. If a pregnancy test is positive the patient will be discontinued from the study, and the investigator must contact the Shire Medical Monitor.

Pregnancy is not to be reported as an AE; the Pregnancy Reporting Form, found in the Study Operations Manual along with instructions for completion, should be used to report the pregnancy. The pregnancy will be followed up through delivery or final outcome.

7.26 Removal of Patients from the Trial or Study Drug

The patient's parent or legally authorized representative acting on behalf of the patient is free to withdraw consent and discontinue participation in the study at any time without prejudice to further treatment. Since this is an extension trial, there will be no replacement of patients who discontinue the study for any reason.

A patient's participation in the study may be discontinued at any time at the discretion of the investigator, sponsor, or medical monitor. The following may be justifiable reasons for the investigator, sponsor, or medical monitor to remove a patient from the study:

- Adverse Event: If a patient experiences an AE which, in the judgment of the investigator, the sponsor, or the medical monitor, presents an unacceptable consequence or risk to the patient.
- Adverse Laboratory Experience: If a patient has an adverse laboratory experience which, in the judgment of the investigator, the sponsor, or the medical monitor, presents an unacceptable consequence or risk to the patient, the patient may be withdrawn from the study.
- Comorbidity: If a patient develops comorbidity during the course of the study that is independent of the study indication, and treatment is required that is not consistent with protocol requirements.
- Intercurrent Illness: If a patient develops an illness during the course of the study that is not associated with the condition under study, and which requires treatment that is not consistent with protocol requirements.
- Refusal of Treatment: If the patient, the patient's parent(s) or legally authorized representative(s) discontinues participation in the study, or the patient is discontinued by the investigator, reasonable efforts will be made to follow the patient through the end of study assessments. The reason for refusal will be documented on the eCRF.

- Withdrawal of Informed Consent: A patient's parent or legally authorized representative may withdraw his informed consent to participate in the study at any time.
- Cerebrospinal fluid leukocyte count >100 cells per cubic millimeter for 2 consecutive months.
- New onset seizure.
- Anaphylactic reaction beyond reasonable management as described in the Investigator's Brochure.
- Clinically problematic intubations or extubations, which may preclude safe airway management and anesthesia.
- Development of refractory spinal fluid leakage.
- Clinically significant prolonged (eg, greater than 24 to 48 hours) worsening in mental status, including development of new focal or non-focal neurological symptoms, or recurrence of a previously stable prior medical problem judged due to study drug or participation that is exclusive of effects from anesthesia.
- Non-compliance, including failure to appear at 1 or more study visits.
- The patient was erroneously included in the study.
- The patient develops an exclusion criterion.
- The study is terminated by the sponsor.
- The patient becomes pregnant during the trial.

If a patient discontinues the study the Patient Completion/Discontinuation eCRF describing the reason for discontinuation must be completed. Any AE's experienced up to the point of discontinuation must be documented on the AE eCRF.

If AEs are present when the patient withdraws from the study, the patient will be re-evaluated within 30 days of withdrawal. All ongoing SAEs at the time of withdrawal will be followed until resolution.

At the time of discontinuation or withdrawal, patients will be asked to participate in all safety and efficacy evaluations required for the end of study visit and for the safety follow-up visit for the treatment period of the study. Participation in these EOS procedures will be strongly encouraged, but is voluntary for those patients electing to discontinue from the study. The patient should be scheduled for the removal of the IDDD. The final evaluation in the safety follow-up period for patients who do not have the IDDD removed (full or partial device) is defined as the follow-up evaluation performed for up to 3 years after the treatment period ends.

7.27 Study Discontinuation Process

If the patient is discontinued from the study, the IDDD should be removed and a modified end of study visit should be completed within 30 days after withdrawal. These visits may be combined into one visit, in which case follow-up via a phone call should be completed within 14 days after the device removal to collect safety information. The end of study visit only requires collection of safety assessments, including symptom-directed physical exam, vital signs, clinical laboratory tests (hematology, serum chemistry, and urinalysis), concomitant medications, therapies, and procedures, and AE monitoring. No MRI or cognitive assessments are required. No study-required CSF collection is needed at the IDDD removal, unless required for AE resolution.

If the investigator determines that the IDDD should not be removed from the patient based upon a safety assessment and the IDDD (full or partial) remains in the patient, then the patient will continue in the study under the safety follow-up period upon completion of their last treatment period visit. This last treatment period visit only requires collection of safety assessments, including symptom-directed physical exam, vital signs, clinical laboratory tests (hematology, serum chemistry, and urinalysis), concomitant medications, therapies, and procedures, and AE monitoring. No MRI or cognitive assessments are required. No study-required CSF collection is needed at the IDDD removal, unless required for AE resolution. Once the patient completes their last treatment period visit, they will return for their first safety follow up visit in six months. The patient will continue in the safety follow-up period with a clinic visit every 6 months for up to 3 years or until the device is removed in the last patient. An end of study follow-up via a phone call should be completed within 14 days after the device removal to collect safety information (refer to Section 8.5).

7.28 Other Study Procedures

This section is not applicable.

7.29 Appropriateness of Measurements

The neurocognitive and developmental assessments are intended to gauge which domains can be accurately measured, with which specific tools, despite the considerable behavioral and cognitive challenges in Sanfilippo syndrome. The evaluation of these domains and the analysis of CSF, serum, and urine biomarkers may provide the pivotal data necessary to inform the clinical assessments and biomarkers used in possible future Sanfilippo syndrome ERT trials.

8 STUDY ACTIVITIES

Patients who participated in Study HGT-SAN-055 through Week 26 and completed the EOS evaluations may be eligible for enrollment in this open-label extension study. Informed consent (and assent, if applicable) must be obtained prior to performing any study related procedures that are specific to HGT-SAN-067. Informed consent may be obtained anytime from Week 20 in HGT-SAN-055. This would allow a patient to have a nonfunctional IDDD replaced or revised prior to the first HGT-1410 dose in HGT-SAN-067.

8.1 Screening Visit/Study Start Visit – Main Site

All Screening assessments for this study are to have been performed during the Week 26 EOS procedures in HGT-SAN-055 (ie, 30 [\pm 7] days after the last HGT-1410 administration). If less than 60 days have elapsed since completion of the EOS assessments for HGT-SAN-055, and the start of HGT-SAN-067, the assessments detailed in this Screening visit do not need to be repeated. The Baseline visit for this study will be the first day the patient received their first dose of HGT-1410 in the HGT-SAN-055 Study.

If more than 60 days have elapsed following the HGT-SAN-055 EOS procedures, patients will be evaluated for enrollment in HGT-SAN-067 on a case-by-case basis by the investigator. A decision about enrollment will be made following discussion with the medical monitor. If the patient is enrolled, the following assessments are to be repeated within 30 days prior to the first scheduled intrathecal HGT-1410 dose:

- Physical examination
- Height and weight
- Head circumference
- ECG
- Vital signs
- Hematology
- Leukocyte pellet preparation to be used for additional disease-related laboratory studies, including possible assessment of cross-reactive immunologic material (if this is not collected at baseline, it can be collected at any subsequent pre-dosing time point)
- Serum chemistry
- Pregnancy testing (for post menarche premenopausal females only)
- Urinalysis
- Urine GAG, including heparan sulfate and heparan sulfate derivatives
- Plasma collection for biomarkers
- Anti-rhHNS antibody testing (serum and CSF)
- General anesthesia: administration of anesthesia will be given prior to the following assessments:
 - ABR
 - MRI of the head
 - Neurological examination (performed prior to the administration of anesthesia)

- Full Neurodevelopmental assessments, including Vineland Adaptive Behavior Scales, Second Edition (VABS-II; all assessments performed prior to the administration of anesthesia)
- CSF sample collection (chemistry, cell count, heparan sulfate and heparan sulfate derivatives, and other MPS exploratory biomarkers) via the IDDD
- Children's Sleep Habits Rating Scale
- CHQ-50
- CHQ-87
- ITQOL
- Concomitant medications, therapies, and procedures
- AE assessments

8.2 Treatment: Drug Administration and Weekly Assessments – Main or Local Site

Patients will receive HGT-1410 IDDD monthly (Q4W), on Day 2 (± 2 days), Week 1.

Patient assessments for safety, biochemical, and neurological baseline measures (Day 1, Week 1) will occur on the day before the first IT injection. Note: Day 1 assessments may be performed on the same day as the administration of study drug (Day 2). This can occur if it is feasible for the patient to arrive at the study site early in the day, and if it is deemed clinically appropriate by the investigator. If the procedures on Day 1 and Day 2 are combined in this way, the assessments will be recorded as occurring on Day 2.

CSF samples will be obtained from these patients on Day 2, immediately prior to the first IT study drug injection.

8.2.1 Week 1

8.2.1.1 Day 1 (Pre-treatment) Assessments Performed Prior to Each Dose

- Physical examination
- Height and weight
- Vital signs (may be performed on Day 2 if feasible for the patient to arrive at the study site early in the day and if deemed clinically appropriate by the investigator)
- Hematology (after Month 54 frequency reduced to Q3 Months)
- Serum chemistry (after Month 54 frequency reduced to Q3 Months)
- Urinalysis (after Month 54 frequency reduced to Q3 Months)
- Pregnancy testing (applicable females only)
- Neurological examination (to be performed if symptom directed prior to the administration of anesthesia and the HGT-1410 IT injection and at a minimum of every 12 months)
- Concomitant medications, therapies, and procedures
- AE assessments

Note: If the HGT-SAN-055 EOS (or HGT-SAN-067 Screening) assessments were performed within 7 days of first intrathecal HGT-1410 treatment in this study, the pre-treatment assessments described in this section do not need to be completed prior to the first treatment in study HGT-SAN-067.

DAY 1 (PRE-TREATMENT) ADDITIONAL ASSESSMENTS PERFORMED AT MONTHS 12, 24, 36, 54, 60, 72, 84, 96, AND 102

- Head circumference
- Visual and hearing assessments
- Urine GAG, including heparan sulfate and heparan sulfate derivatives (performed at Months 60, 66, 72, 78, 84, 90, and 96, ie, Q6 Months following Month 54)
- Plasma collection for biomarkers
- Anti-rhHNS antibody testing (performed at Months 60, 66, 72, 78, 84, 90, and 96, ie, Q6 Months following Month 54)
- ABR (not performed after Month 54, ie not on Months 60, 66, 72, 84, 96, or 102)
- MRI of the head
- Full neurodevelopmental testing, including VABS-II (performed prior to the administration of anesthesia and the HGT-1410 IT injection)
- Children's Sleep Habits Rating Scale
- Child health questionnaire-50
- Child health questionnaire-87
- Infant toddler QoL Questionnaire

8.2.1.2 Day 2 (± 2 days) Assessments and Administration of HGT-1410

Patients may be discharged from the clinical site 4 hours after dosing, if deemed stable by the investigator.

- Physical examination (after Month 54 the full physical examination will be performed on an annual basis at Months 66, 78, 90, and 102. The remainder of the physical examinations will be symptom-directed.)
- ECG (performed following IT study drug injection)(after Month 54 performed Q3 months)
- Vital signs (to be performed at the discretion of the investigator)
- CSF sample collection (obtained prior to IT study drug injection)
- HGT-1410 IT injection (Day 2 ± 2 days)
- Neurological examination (to be performed if symptom directed and at a minimum of every 12 months)
- Concomitant medications, therapies, and procedures
- AE assessments

The neurological exam should not occur sooner than 4 hours after study drug administration or before the patient has fully recovered from any anesthesia administered for the dosing, whichever occurs later.

8.3 End of Study/Early Termination Procedures for Treatment Period: Month 103 – Main Site

Patients who complete the study or who discontinue prior to the end of the study during the treatment period, will have EOS assessments performed 30 (± 7 days) after their last dose of HGT-1410.

Patients who discontinue or are withdrawn prior to study completion will be asked to participate in the EOS procedures at the time of discontinuation for the treatment period of the study. Participation in these EOS procedures will be strongly encouraged, but is voluntary for those patients electing to discontinue from the study. Note: Patients should have the IDDD removed when they discontinue from the treatment period of the study, unless the Investigator determines that it should not be removed based upon safety assessments. The device can remain in the patient (partial [catheter only] or full [port, catheter, and suture wings]) if the patient is doing clinically well and there are no further known risk factors such as infection (eg, meningitis). The device may be partially or fully removed as medically required and determined by the neurosurgeon at a future date.

Physical examination

- Height and weight
- Head circumference
- Visual and hearing assessment
- ECG
- Vital signs
- Hematology
- Serum chemistries
- Urinalysis
- Pregnancy testing (applicable females only)
- Urine GAG, including heparan sulfate and heparan sulfate derivatives
- Plasma collection for biomarkers
- Anti-rhHNS antibody testing (serum and CSF)
- MRI of the head (unless performed at Month 102)
- CSF sample collection (unless performed at Month 102)
- Neurological examination
- Full neurodevelopmental testing, including VABS-II
- Children's Sleep Habits Rating Scale
- CHQ-50
- CHQ-87
- Infant toddler QoL Questionnaire
- Concomitant medications, therapies, and procedures
- AE assessments

All patients who discontinue the study early should have their IDDD removed, unless, as indicated above, the Investigator determines that it should not be removed based upon safety assessments.

During the treatment period, patients who withdraw or discontinue after having received fewer than 3 IT injections will not need to complete the EOS visit.

Patients who withdraw or discontinue from the study after having received 3 or more IT injections, will be asked to complete the EOS visit and undergo all the scheduled assessments.

8.4 Safety Follow-up (by Telephone or Visit) Month 104

Patients who complete the study or withdraw early will have a safety follow-up telephone call or visit 30 Days (± 7 days) after the last study visit. This will assess:

- Concomitant medications, therapies, and procedures
- AE assessments

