In the event of a device malfunction, X-rays may be performed to investigate, as well as to verify correct catheter and port placement following surgical IDDD implantation or revision. In addition, fluoroscopy may be employed intra-operatively to guide catheter placement. Patients may undergo 3 X-ray examinations in association with each episode of IDDD malfunction and subsequent IDDD revision or replacement. The number of IDDD revisions/replacements is limited to 2 in any 6-month period (including the time in the HGT-SAN-055 study), and the number of protocol-associated X-ray evaluations is limited to 6 exposures in any 6-month period (including time in study HGT-SAN-055).

Patients will be evaluated for safety throughout the study. Adverse events that occur in HGT-SAN-055 and are ongoing at enrollment in HGT-SAN-067 will be captured as ongoing in the HGT-SAN-055 study and also be reported as a concurrent condition in the HGT-SAN-067 eCRFs. Specific safety stopping criteria will be applied and will be based on the types and severity of AEs reported while on-study. These data will be reviewed to inform the decision to discontinue a patient, a dose group, or the study as a whole.

All patients will have an EOS visit during the treatment period, 30 (± 7) days following their last administration of HGT-1410 (ie, Month 102). The EOS procedures will include standard clinical laboratory tests (serum chemistry, hematology, and urinalysis) in CSF and blood, protocol specific laboratory testing (eg, anti-rhHNS antibody testing), neurodevelopmental testing, child

health questionnaires, and MRI. Use of concomitant medications, therapies, and procedures will be recorded and AEs will be monitored.

All patients will be contacted by telephone or will have a visit for a Final Safety Follow-up, conducted at 30 (± 7) days after the EOS visit, of the treatment period, (ie, Month 103) to collect updated information on AEs and concomitant medications, therapies, and procedures.

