6.3.1 Cerebral Spinal Fluid Sample Procedure

CSF samples will be obtained prior to each injection for clinical laboratory evaluation and potential biomarker studies. The IDDD will be used for CSF sampling and a topical anesthetic agent may be applied over the skin covering the IDDD reservoir prior to sampling. Site personnel should refer to the operations manual for instructions on the use of topical anesthesia prior to accessing the IDDD reservoir.

If use of the IDDD is precluded on a scheduled day of dosing, CSF samples may be obtained by LP, as described in the IDDD Manual and Section 6.3.2. Intrathecal Administration of HGT-1410.

A visual examination of both the port and catheter track will be performed before each IT injection.

HGT-1410 will be administered using an IDDD. After appropriate pre-procedure assessments are completed, anesthesia cream will be applied to the skin over the port. Patients may receive sedation as necessary to alleviate anxiety and/or to facilitate drug delivery.

Patients will receive HGT-1410 via slow push/injection through an appropriately sized syringe (see the Pharmacy Manual). Replacement of fluid, including drug, to the CSF will be an approximate equal volume to that removed. The patient's vital signs will be continuously monitored. The patient will also be monitored closely during study drug administration and through the next 4 hours for any adverse clinical reactions. The patient will be encouraged to lie down comfortably for 1 to 3 hours post injection, although this may be difficult for the most hyperactive patients.

For the Soph-A-Port Mini S, a 22-gauge Huber non-coring needle is to be used for access to the implanted port; standard hypodermic needles would damage the septum and may cause leakage. If no needle-free connector is present, either a stopcock of the Huber needle infusion set's clamp is to be used to prevent CSF backflow and to mitigate the risk of air entering the system. It is possible to use other brands of Huber non-coring needles, provided that their specifications are identical to that of the Huber needle supplied by Sophysa in the SOPH-A-PORT Mini S (22G).

The injection date, injection start/stop time, planned dose, injection volume, and flush volume will be recorded on the patient's eCRF.

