7.7.6 Cerebrospinal Fluid Assessments

Cerebrospinal fluid sample collection, processing, and shipping instructions will be provided in the Laboratory Manual. A CSF sample will be reserved for possible exploratory biomarker studies for MPS IIIA disease.

Each CSF sample collected will be assessed for appearance and will be analyzed using the assays listed in Sections 7.7.6.1, 7.7.6.2, and 7.7.6.4. In addition, as more is learned about Sanfilippo CNS pathology and etiology, future exploratory assays of CSF metabolites, protein or ribonucleic acid (RNA) may become used as they become available in the future.

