Appendix 1 Schedule of Events

Table A1-1 HGT-SAN-067 Study Assessments for Patients Who Have Received 6 Months of HGT-1410 Treatment in Study HGT-SAN-055

Assessment	Month 7 through Month 104 (from the start of HGT-SAN-055)							
		Dosed every 28 (±7) days (ie, Q4W)						
	Screening/or HGT-SAN-055 EOS Visit ^l (Month 6 from the start of HGT-SAN-055)	Pre-Tx Day 1 ^a	IT dosing Day 2 (±2)	Months 12, 24, 36, 54, 60, 72, 84, 96 and 102 (from the start of HGT-SAN-055)	Additional Assessments at Months 66, 78, and 90 (from the start of HGT-SAN-055)	Months 9, 15, 18, 21, 27, 30, 33, 39, 42, 45, 48, and 51 (from the start of HGT-SAN-055)	EOS ^c Month 103 (from the start of HGT-SAN-055)	Month 104 Safety Follow-up ^f
	Main Site only	Main or Local Site	Main or Local Site	Main Site only	Main Site only	Main Site only	Main Site only	
Informed Consent/Enrollment		•						
Physical Examination	•	• ^p	• ^p	• ^p				
Symptom-Directed Physical Examination		• ^p	• ^p				•	
Neurological Examination ^h	•	• ^s	• ^s				•	
Height and Weight	•	•					•	
Head Circumference	•			•			•	
Visual and Hearing Assessment				•			•	
ECG	•		• ^b				•	
Vital Signs	•	• ^s	• ^s				•	
Hematology	•	•					•	
Serum Chemistry	•	•					•	
anti-rhHNS antibody testing (serum) ^k	•			• ^t	• ^t		•	
Plasma storage for biomarkers	•	•		•			•	
Pregnancy Testing ^l	•	•					•	

Table A1-1 HGT-SAN-067 Study Assessments for Patients Who Have Received 6 Months of HGT-1410 Treatment in Study HGT-SAN-055

Assessment	Month 7 through Month 104 (from the start of HGT-SAN-055)							Month 104 Safety Follow-up ^f
	Dosed every 28 (±7) days (ie, Q4W)			Months 12, 24, 36, 54, 60, 72, 84, 96 and 102 (from the start of HGT-SAN-055)	Additional Assessments at Months 66, 78, and 90 (from the start of HGT-SAN-055)	Months 9, 15, 18, 21, 27, 30, 33, 39, 42, 45, 48, and 51 (from the start of HGT-SAN-055)	EOS ^c Month 103 (from the start of HGT-SAN-055)	
	Screening/or HGT-SAN-055 EOS Visit ⁱ (Month 6 from the start of HGT-SAN-055)	Pre-Tx Day 1 ^a	IT dosing Day 2 (±2)					
Urinalysis	•	•					•	
Urine GAGs	•			• ^t	• ^t		•	
Leukocyte pellet preparation ^m	•							
CSF chemistry and cell counts ^c	•	•					•	
CSF sample storage ^{c,o}	•	•					•	
CSF Heparan Sulfate and Heparan Sulfate Derivatives ^c	•			• ^t	• ^t	•		
Anti-rhHNS antibody testing (CSF) ^c	•			• ^t	• ^t		•	
Auditory Brainstem Response (ABR) ^q	•			•				
MRI of the Head	•			•			• ⁿ	
HGT-1410 dosing: every 28 (±7) days ^{d,g}			•					
Full Neurodevelopmental Testing ^l	•			•			•	

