Children's Sleep Habits Rating Scale	•			•			•	
Child Health Questionnaire-50	•			•			•	
Child Health Questionnaire-87	•			•			•	
Infant Toddler QOL Questionnaire	•			•			•	

Table A1-1 HGT-SAN-067 Study Assessments for Patients Who Have Received 6 Months of HGT-1410 Treatment in Study HGT-SAN-055

Assessment	Month 7 through Month 104 (from the start of HGT-SAN-055)							
	Dosed every 28 (±7) days (ie, Q4W)							
	Screening/or HGT-SAN-055 EOS Visit ⁱ (Month 6 from the start of HGT-SAN-055)	Pre-Tx Day 1 ^a	IT dosing Day 2 (±2)	Months 12, 24, 36, 54, 60, 72, 84, 96 and 102 (from the start of HGT-SAN-055)	Additional Assessments at Months 66, 78, and 90 (from the start of HGT-SAN-055)	Months 9, 15, 18, 21, 27, 30, 33, 39, 42, 45, 48, and 51 (from the start of HGT-SAN-055)	EOS ^c Month 103 (from the start of HGT-SAN-055)	Month 104 Safety Follow-up ^f
Main Site only	Main or Local Site	Main or Local Site	Main Site only	Main Site only	Main Site only	Main Site only		
Concomitant Medications, Therapies, and Procedures	•	•	•				•	•
Adverse Event Monitoring	•	•	•				•	•

Abbreviations: ABR = Auditory brainstem response; CSF = cerebrospinal fluid; EOS = end of study ; ECG = electrocardiogram; IT = intrathecal; MRI = Magnetic resonance imaging; TX = treatment

Note: The timing of assessments is calculated from the start of HGT-SAN-055. Therefore, for example, the end-of-study visit, as presented here at Month 102, corresponds to Month 102 in HGT-SAN-067, but represents a total of 102 months of study treatment (102 months in HGT-SAN-067 + 6 months in HGT-SAN-055).

^a Week 1 only, and only performed if >7 days have elapsed since HGT-SAN-055 EOS visit assessments.

^b ECG to be performed following administration of study drug, after Month 54 it is to be performed every 3 months.

^c CSF samples will be obtained according to the process within the study laboratory manual. An attempt will be made to obtain a CSF sample via the IDDD prior to each administration of HGT-1410 and at the End of Study visit. If it is not possible to obtain a CSF using the IDDD, the IDDD may be replaced (up to twice in a 6 month period [including the time in the HGT-SAN-055 study]) or an LP may be performed.

^d Patients may be discharged as early as 4 hours post HGT-1410 infusion (ie, on Day 2) when deemed clinically stable by the investigator.

^e All patients who complete the study will have end of study assessments performed 30 (±7 days) after their last dose of study drug.

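### Section 8.3 waives the end-of-study CSF sample whenever the routine pre-dose Month 102 sample was obtained, contradicting Table A1-1 and leaving no scheduled CSF safety sample after the final dose

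*Protocol*

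**What the plan says.** Section 8.3 lists the EOS procedures for the treatment period. Its CSF line reads "CSF sample collection (unless performed at Month 102" (closing bracket omitted here). Two lines higher, with no exception attached, the same list has "Anti-rhHNS antibody testing (serum and CSF" (bracket likewise closed in the source).

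Sampling during treatment is set out in three places:

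- Section 6.3.1: "CSF samples will be obtained prior to each injection for clinical laboratory evaluation and potential biomarker studies".
- Section 8.2.1.2, the Day 2 list: "CSF sample collection (obtained prior to IT study drug injection".
- Table A1-1, footnote c: CSF is to be attempted "prior to each administration of HGT-1410 and at the End of Study visit".

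Section 4.1 places the EOS visit 30 (± 7) days "following their last administration of HGT-1410 (ie, Month 102".

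In Table A1-1 the EOS column is marked for CSF chemistry and cell counts, CSF sample storage and CSF antibody. None of those marks carries footnote n, which drops an assessment from the Month 103 visit if it was done at Month 102. In the EOS column that footnote is attached to MRI alone. The row "CSF Heparan Sulfate and Heparan Sulfate Derivatives" has no EOS mark.

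Section 3.1 names CSF chemistries (with cell counts and inflammatory markers) and anti-rhHNS antibodies in CSF and serum among the primary safety endpoints.

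**The concern.** A waiver of this kind makes sense if the earlier assessment can replace the later one. For CSF it cannot. The Month 102 sample is taken just before the last injection, and the EOS sample is the first one scheduled after it. Because a pre-dose sample is routine at every injection, the condition is satisfied almost by construction, and a line that looks like protection against duplication works as a cancellation.

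No later visit recovers the information. The Month 104 contact covers adverse events and concomitant treatment only. In the follow-up of patients with a retained device (Section 8.5, Table A1-2), CSF laboratory tests are done only when a device-related adverse event calls for them. A raised cell count or a CSF antibody response arising after the final dose would therefore have no scheduled sample to reveal it, and a raised count first seen at Month 102 would have no scheduled repeat. A site also cannot follow both the CSF line and the CSF antibody line of Section 8.3.

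**Working it through.** The protocol states no figure on this point, so the check is a comparison of schedules with a short count.

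**1. When is the last dose, and when is EOS?** Section 4.1 can be read as dating either the last dose or the EOS visit to Month 102, and the note under Table A1-1 places EOS at Month 102. The title of Section 8.3 and the EOS column of the table give Month 103. Taking the last dose at Month 102 and EOS at Month 103, EOS falls 30 − 7 = 23 to 30 + 7 = 37 days after the last dose.

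**2. Is the waiver condition met?** Sections 6.3.1 and 8.2.1.2 and footnote c all put a CSF sample before each injection, so also before the one at Month 102. Footnote c describes an attempt. The condition is met for each completer whose Month 102 attempt succeeded.

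**3. Scheduled CSF samples after the last dose, for such a completer**

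| Source | Samples after last dose |
|---|---|
| Section 8.3, CSF line | 0 |
| Section 8.3, antibody line | 1 (antibody) |
| Table A1-1 and footnote c | 1 (chemistry, cell counts, storage, antibody) |

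**4. How much of the treatment period is affected?** Assume one dose per named month from Month 7 to Month 102: 102 − 7 + 1 = 96 doses. Each of the first 95 is followed by the next pre-dose CSF sample at about 28 (± 7) days. Only the 96th has no later sample under the waiver.

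**5. CSF antibody.** Footnote t and Section 8.2.1.1 name Months 60 to 96, every 6 months, for antibody testing after Month 54. Month 102 is not in that list, although the table column and the section's sub-heading include it. On the named months, without an EOS sample the last CSF antibody result would date from Month 96, which is 102 − 96 = 6 months before the last dose.

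**6. Heparan sulfate.** Table A1-1 leaves the EOS cell empty. Section 7.7.6 says: "Each CSF sample collected will be assessed for appearance and will be analyzed using the assays listed in Sections 7.7.6.1, 7.7.6.2, and 7.7.6.4". Section 7.7.6.2, one of those listed, is the heparan sulfate assay. If an EOS sample is taken, the text calls for the assay and the table does not schedule it.

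**7. Patients who discontinue.** Section 8.3 asks those with 3 or more injections to complete EOS with all scheduled assessments, and Section 7.26 asks for all EOS safety and efficacy evaluations. Section 7.27 restricts the visit to safety assessments, does not list CSF among its laboratory tests, and requires no study CSF at device removal unless an adverse event needs it. These three do not agree.

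**The case against.** The strongest case against is that little is lost. Every earlier dose is followed by a CSF sample, adverse events are still collected at EOS and Month 104, Section 7.13.3 allows CSF to be sampled for clinical concerns, and the analysis is descriptive. The draw is also not trivial: if the device cannot be used, footnote c allows device replacement or lumbar puncture, and Section 7.8 provides for anesthesia or sedation. All of this stands and limits the size of the point. It does not remove the contradiction.

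Footnote n is worded in the plural although in the EOS column it sits on one row, which might suggest that it was once meant to reach further. Section 4.1 is weak support the other way: it mentions laboratory tests in CSF at EOS without naming cell counts or antibody. Footnote c, however, states EOS sampling directly.

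A reader might infer more than the documents support:

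- *No completer would have CSF data after the last dose, or all 12 patients lose it.* Month 102 sampling is an attempt, and a completer whose sample failed would still be sampled at EOS. Twelve is the enrolment ceiling, not a count of completers.
- *The antibody test is waived.* Section 8.3 still lists it, so the section contradicts itself.
- *Section 8.3 contradicts the table on heparan sulfate.* The table has no EOS mark there. The conflict is between the table and Section 7.7.6.
- *Early stoppers have stored CSF but no final heparan sulfate value.* Sections 7.7.6 and 7.7.6.2 cover any sample that is taken, and under Section 7.27 there may be none.

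**Conclusion.** The inconsistency is real. The CSF line in Section 8.3 conflicts with Table A1-1 and footnote c, and with the antibody line in its own list. A completer whose pre-dose Month 102 sample was obtained has, under that line, no scheduled CSF chemistry or cell count after the last dose, where the table schedules one.

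The loss is one time point per such completer, confined to the interval after the final dose, on primary safety endpoints. The conclusion assumes that the last dose is at Month 102 and EOS at Month 103. How many patients are affected cannot be stated, because the number of completers and the success of the Month 102 sampling are not given. The empty heparan sulfate cell is a separate and minor inconsistency.

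**What to change.** Reconcile the CSF line in Section 8.3 with Table A1-1 and footnotes c and n, so that the Month 102 exception covers only the assessment carrying footnote n (MRI) and a pre-dose sample does not cancel the EOS CSF safety and antibody sample that the table already schedules. Reconcile Section 7.27 with Sections 7.26 and 8.3 on whether EOS CSF is expected from patients who discontinue. As a minor item, bring the empty EOS cell for CSF heparan sulfate into line with Sections 7.7.6 and 7.7.6.2.

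The editorial cost is a phrase in Section 8.3, one table cell and the alignment of Section 7.27. The practical cost is one CSF collection per completer that a site following Section 8.3 would have skipped, which may need lumbar puncture or sedation if the device cannot be used.
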